10.1. General Information

Study information is collected on study-specific eCRFs by the site. Study monitoring will occur at regular intervals to ensure the protection of subject rights and safety, data integrity and accuracy, and proper study conduct in compliance to the protocol and applicable regulations including 21 CFR 312 and ICH E6 GCPs. Study visits and telephone assessments must occur with the window specified in **Table 10-1**; visits and calls out of window or missed are to be reported as protocol deviations. The study-required procedures are to be conducted as shown in **Table 10-1**.

Timely and complete follow-up visits will ensure the scientific integrity of the data is maintained and allow for continued oversight of subject safety.

Table 10-1 Schedule of Events

Activity	Screening (Enrollment)	Baseline / Enema Administration (≤ 21 days from Screening)	Follow-up Visits: 1- and 8-Week (± 3 days) Assessments ¹	Follow-up Phone Assessment: Week 4 (± 3 days)	Follow-up Phone Assessment: 4 and 6 months (± 14 days)	Unscheduled Possible Recurrence Visit	Second Enema Administration ¹ (≤ 21 calendar days post Tx Failure)	Second Enema Follow-up Phone Assessment: 1-, 4-, and 8-weeks (± 3 days), and 6 months (± 14 days)
Informed consent obtained	X							
Demographics, medical history	X							
Prescribe/continue antibiotics for CDI symptom control	X							
Physical exam	X							
Stool sent to Rebiotix by subjects for testing and archiving (optional)	X		X	X	X	X		X
Central Lab CBC w/differential testing ³	X ³	X						
Central Lab CD4 testing	X ³							
Central Lab CMP & CRP testing	X							
C. difficile testing ⁴						X ⁴		
Central Lab stool and blood testing		X						
Urine pregnancy testing performed at site (if applicable)	X	X					X	
Cdiff32 Questionnaire	X		X		X	X		
Inclusion/exclusion criteria confirmed	X	X						
24-72hr washout period confirmed		X					X ⁷	
Enema administered		X					X	
Product complaint (if applicable)		X					X	
CDI symptoms assessed		X	X	X	X	X	X	X
Vital signs assessed	X	X				X	X	
Weight	X		X	X	X			X
Subject Diary discussed/reviewed	X	X	X ⁵					
Employment status assessed	X		X ⁶		X			
Concomitant medications	X	X	X	X	X	X	X	X
Adverse events assessed		X	X	X	X	X	X	X
Solicited events assessed ²		X	X ²					

¹ Documented treatment failures may receive a second RBX2660 enema.

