10.13. Unscheduled Possible Recurrence Visit

If CDI recurrence is suspected any time within 8 weeks of the last study enema due to new onset documentation of three or more unformed/loose (i.e., Bristol Stool Scale type 6-7) stools within 24 or fewer consecutive hours for at least two consecutive days, possible treatment failure should be assessed. An in-office visit should occur if a recurrence of CDI is suspected. The subject must provide a fresh stool sample for shipment to the central laboratory to test for the presence of *C. difficile*.

The following study activities/data will be collected at the Unscheduled Possible Recurrence visit:

- Collect fresh stool sample to send to the central laboratory for analysis
- Assess recurrence of CDI
 - Start date of symptoms, current symptoms, central laboratory testing result, source of episode (*CDI recurrence, healthcare contagion, community contagion, or unknown*), treatment(s)
- Vital signs: temperature, pulse, blood pressure, respiration
- Adverse event collection, including the new onsets of obesity, metabolic syndrome, pre-diabetes, diabetes and/or autoimmune disorders
- Changes to concomitant medications since last visit
- Cdiff32 health-related quality of life questionnaire
- For subjects who consented to the Optional Stool Sample collection, remind the subject to collect and ship a stool sample to Rebiotix.

Treatment failure (CDI recurrence) is defined as:

- The presence of CDI diarrhea within 8 weeks of administration of a study enema, which includes a positive stool test for *C. difficile* as determined by the central laboratory.

To ensure consistency across clinical sites for the determination of study failure, the central laboratory will perform the required C. DIFF QUIK CHEK COMPLETE® Test (QCC Test) rapid enzyme immunoassay test for glutamate dehydrogenase (GDH) and toxins A and B.

In the case of suspected treatment failure where there is an immediate concern for subject safety, including the potential for serious adverse events, a test may be conducted at the site or other laboratory known to the site **in addition to** sending a sample to the central laboratory for testing. In the event the test results from the central laboratory differ from that of a local laboratory, the results from the central laboratory will be used in determination of treatment failure and eligibility to receive a second treatment with RBX2660, instead of the other laboratory's result.

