5.2 Time Point Algorithms

5.2.1 *Relative Day*

The date of study enema administration will be considered relative day 1, and the day before study enema administration will be relative day -1. Relative days will be calculated as follows only when the full assessment date is known (i.e., partial dates will have missing relative days, unless imputation methods have been specified):

For days before first enema:

Date of Assessment – Date of first enema administration

For days on or after first enema:

Date of Assessment – Date of first enema administration +1

For the purpose of statistical analysis, the analysis visit windows will be calculated in terms of study days since the day of the study enema administration, as illustrated in the following tables:

Table 1. Analysis Windows for Clinical Visits

Visit	Scheduled Study Day	Visit Window in Protocol (Days)	Visit Window for Analysis (Days)
Screening Visit	-20 through -1	-20 through -1	-20 through -1
Baseline/1 st Enema	1	1	1
1-week Office	8	5 - 11	5 - 11
8-weeks Office	57	54 - 60	54 - 60

Table 2. Analysis Windows for Phone Assessments

Visit	Scheduled Study Day	Visit Window in Protocol (Days)	Visit Window for Analysis (Days)
4-weeks - Phone	29	26 - 32	26 - 32
4 months - Phone	121	106 – 134	106 – 134
6 months - Phone	181	166 – 194	166 – 194

Table 3. Analysis Windows for Adverse Event Reporting by Onset Interval

Onset Interval Name	Onset Interval Analysis Window	Window for Analysis (Days)
Baseline	Screening - < Baseline	≤ -1
1-week	Baseline - 1-week	1 through 8
4-week	> 1-week - 4-week	9 through 29
8-week	> 4-week - 8-week	30 through 57
0-8-week	Baseline - 8-week	1 through 57
4-month	> 8-week - 4-month	58 through 121
6-month	> 4-month - 6-month	122 through 180+
8-week-6-month	> 8-week - 6-month	58 through 180+

If a subject has more than one assessment occurring in the same visit window, the data from the visit closest to the scheduled study day will be used for analysis. If two visits have the same distance from the scheduled study day, i.e., one visit occurs -1 day from study day, and the other visit occurs +1 day from study day, the data from the visit after the scheduled study day will be used for analysis.

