6.6 Safety Analysis

The SP will be used to summarize all adverse event data, unless otherwise specified. Safety data will be summarized for events after the first and second enemas, as well as combined. Events occurring after the first enema will be counted up to the date of retreatment, or study exit. Events on, or after, the date of a second enema will be assigned to the second period. The combined analysis will consider all events, after first enema through study exit, even if a subject receives a second enema.

6.6.1 *Analyses Supporting the Primary Safety Endpoint*

Assessment of the primary safety objective will include descriptive statistics and be performed on the SP. Additional sub-analyses of safety data may be performed on sub-populations.

6.6.2 *Other Safety Analyses*

6.6.2.1 *Adverse Events*

A summary of adverse events, TEAEs, non-serious TEAEs, and serious TEAEs will be summarized using counts of the number of events and frequencies (counts and percentages) of

the number of subjects. The incidence of each preferred term (PT) within the primary system organ class (SOC) as well as overall primary SOC incidence will be presented. Summaries may also be presented by PT, irrespective of SOC. A subject with multiple events coded to the same PT within a primary SOC will be counted only once for the PT within the primary SOC. Likewise, a subject with multiple events coded to the same SOC will be counted only once within the SOC.

An overall summary of AEs will present the incidence of (1) all TEAEs, (2) TEAEs related to IP, (3) TEAEs related to enema procedure, (4) TEAEs related to *C. difficile* disease, (5) TEAEs related to a preexisting condition, (6) serious TEAEs, (7) serious TEAEs related to IP, (8) serious TEAEs related to the enema procedure, (9) serious TEAEs related to *C. difficile* disease, (10) serious TEAEs related to a preexisting condition, and (11) TEAEs leading to death.

Frequency of occurrence and number and percent of subjects experiencing an event through 6 months follow-up will be presented for both the first and second enemas as follows:

- All TEAEs
- TEAEs by maximum severity
- TEAEs by relatedness to IP
- TEAEs by relatedness to *C. difficile* disease
- TEAEs by relatedness to enema procedure
- TEAEs by relatedness to preexisting condition
- TEAEs resulting in subject withdrawal
- TEAEs resulting in death
- Serious TEAEs
- Serious TEAEs by maximum severity
- Serious TEAEs by relatedness to IP

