6.7.1.1.1 Recurrence of CDI within 8 weeks of treatment

Recurrence of CDI is defined as the presence of CDI diarrhea within 8 weeks (54-60 days) of administration of a study enema, which includes a positive stool test for *C. difficile* as determined by the central laboratory. A CDI with an onset after 8 weeks (> 60 days) from completion of the study treatment is considered a new CDI. Onset of CDI is the date that the symptoms first started.

The efficacy parameter used to determine treatment success is defined as the absence of CDI diarrhea through 8 weeks after completing a study treatment. Efficacy assessments will occur at each scheduled contact: 1-week, 4-weeks, 8-weeks.

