6.8 Other Endpoints Analyses

Additionally, the other analyses will be conducted on other populations or subgroups as needed.

6.8.1 *Comparison of Baseline characteristics in subjects with treatment success with one dose of RBX2660 vs. those who were unsuccessful.*

A multivariate analysis or regression analysis will be used to identify predictors (if any) for subject success with one RBX2660 dose vs. those who were unsuccessful, for example, age or number of prior CDI events.

6.8.2 *Subject fecal microbial composition at Screening, 1-week, 4-weeks, 8-weeks, 4 months, and 6 months after study treatment.*

Descriptive statistics will be used to present the changes from Screening fecal microbial composition to those at 1-week, 4-weeks, 8-weeks, 4 months, and 6 months after study treatment for those subjects treated with RBX2660.

6.8.3 *Cdiff32 scores at Screening, 1-week, 8-weeks, 4 months, and 6 months.*

Changes from Screening in the Cdiff32 scores will be summarized using descriptive statistics. Last observation carried forward (LOCF) will be used to impute missing post-Baseline data. No inferential statistics will be performed.

6.8.4 *Recurrence of CDI within 8 weeks of second RBX2660 treatment in subjects.*

Determine the treatment success rate of those subjects who received two doses of RBX2660. This success rate will be calculated at 8 weeks following the second RBX2660 enema.

6.8.5 *Concentration of vancomycin-resistant enterococci in stool samples for subjects who were carriers at Baseline.*

Lab generated values for the presence of vancomycin resistant enterococcus based on submitted stool samples at Baseline and at 1-week, 4-weeks, 8-weeks and 4 and 6 months will be assessed for all subjects to identify any trends in the clearance of vancomycin-resistant enterococci following enema treatment.

6.8.6 *Presence of *C. difficile* in stool samples at Screening, 1-week, 4-weeks, 8-weeks, 4 months, and 6 months after study treatment.*

Lab generated values for the presence of *C. difficile* based on submitted stool samples at Baseline and at 1-week, 4-weeks, 8-weeks, 4 months, and 6 months will be assessed for all subjects to identify any trends in the clearance of *C. difficile* following enema treatment.

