7 STATISTICAL METHODS

7.1 General Methodology

Data will be summarized using descriptive statistics with SAS® Version 9.3 or higher. Confidence intervals (CI) will be constructed at the level of 95% unless specified otherwise. For continuous variables, descriptive statistics (number of subjects [N], mean, standard deviation [SD], median, inter-quartile range [IQR], minimum, and maximum) will be generated. For discrete/categorical variables, the number and percentage of non-missing subjects will be generated. Standard operating procedures (SOPs) will be followed in the creation, validation and quality control of all data displays and analyses.

Subject listings of all data from the eCRFs as well as any derived variables will be presented.

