7.3 Handling of Dropouts or Missing Data

No imputations will be used in analyses/summaries. However, a LOCF analysis will be used for evaluation of the Cdiff32 scores. Missing safety data will not be imputed beyond the adjustments for adverse event data mentioned in **Section 6.4.3**.

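### Cdiff32 LOCF makes no exception for a second enema; read literally, most retreated subjects' month-4 and month-6 values would be scores from before retreatment

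*SAP*

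**What the plan says.** Cdiff32 is one of the other endpoints (Protocol 6.7, SAP 5.6), measured at Screening, week 1, week 8, month 4 and month 6. SAP 6.8.3 plans descriptive summaries of change from Screening without inferential statistics, and handles gaps as follows: "Last observation carried forward (LOCF) will be used to impute missing post-Baseline data". SAP 7.3 otherwise rules out imputation but repeats that "a LOCF analysis will be used for evaluation of the Cdiff32 scores". Neither section mentions a second enema.

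On timing, SAP 5.2.1 states that "the analysis visit windows will be calculated in terms of study days since the day of the study enema administration", and its relative-day formulas use the first enema. No restart after retreatment is given. When two assessments share a window, the one nearer the scheduled day is used.

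On collection, Protocol Table 10-1 and the SAP 5.1 table both mark Cdiff32 at the unscheduled visit for possible recurrence. Both leave it blank at the second enema and in the follow-up column, which the protocol table heads "Second Enema Follow-up Phone Assessment: 1-, 4-, and 8-weeks" and 6 months. Protocol 10.14.1 does not list it for those calls. Protocol 7.5 keeps on the original schedule only those failures who do not have a second enema. Protocol 10.12, which mails out the questionnaire for the month-4 and month-6 calls, also dates the last call from the most recent enema.

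For safety events, SAP 6.6 does address retreatment: "Events occurring after the first enema will be counted up to the date of retreatment, or study exit". It plans first-enema, second-enema and combined summaries.

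**The concern.** A retreated subject has no scheduled Cdiff32 after the second enema, yet the month-4 and month-6 summaries need either a value or a rule for its absence. The SAP does not say whether an assessment that was never scheduled counts as missing. The wording of 6.8.3 covers missing post-Baseline data without qualification, so the literal reading is to carry the last available score, which predates retreatment. On the other reading these subjects drop out of the later means, and the SAP does not state that either.

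Evaluating quality of life with Cdiff32 is a named objective (Protocol 6.3, SAP 2.3), and retreated subjects are selected by treatment failure. Many items use a one-week recall (Protocol 17). A carried recurrence-visit score would present the week of recurrence as the state at month 6; a carried week-1 score would hide the recurrence. Either would be mixed with observed scores in one mean, and no pre-specified summary separates the two.

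**Working it through.** The plan gives no figure of its own here to reproduce. The check is a timeline, followed by an illustrative count.

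**Inputs**
- Latest qualifying onset, SAP 6.7.1.1.1: "A CDI with an onset after 8 weeks (> 60 days) from completion of the study treatment is considered a new CDI". Sixty days after the enema is relative day 61.
- Second enema: within 21 calendar days of failure determination (Protocol 10.14).
- Analysis windows (SAP 5.2.1): week 1, days 5–11; week 8, days 54–60; month 4, days 106–134; month 6, days 166–194.

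**Month 4.** A failure determined by day 84 is retreated by 84 + 21 = day 105, before the window opens on day 106. This leaves 84 − 61 = 23 days between the latest qualifying onset and determination (24 if the cut-off is read as relative day 60). Unless determination takes longer than that, every retreated subject is retreated before the month-4 window, with no scheduled Cdiff32 inside it.

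**Week 8.** A failure determined by day 32 is retreated by 32 + 21 = day 53, before the window opens on day 54. Week 8 is affected for early retreatment.

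**Exceptions**
1. The condition in Protocol 10.13, "If CDI recurrence is suspected any time within 8 weeks of the last study enema", covers the second enema too, and Cdiff32 is collected at that visit. It is triggered by symptoms, so a retreated subject without a suspected recurrence gets no such score.
2. If Protocol 10.12 is read as calling for a questionnaire at the 6-month call after a second enema on day D, that score falls in the first-enema month-6 window only if D + 180 ≤ 194, so D ≤ 14 (call on schedule), or D + 166 ≤ 194, so D ≤ 28 (call 14 days early). Month 4 is unchanged. The documents give no distribution of D. A simulation assumed onset times from front-loaded to nearly even over 57 days, plus 2 days for the symptom criterion, 1–10 days to determination and 3–21 days to the enema. It put about 1–2% of retreated subjects at or before day 14 and 14–38% at or before day 28.

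These exceptions do not overturn the word most.

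**Which score is carried.** A recurrence-visit score inside a window, for example on day 60, could become the week-8 value under the closest-visit rule. It would then be carried 121 − 60 = 61 days to month 4 and 181 − 60 = 121 days to month 6. Eligibility for LOCF is unstated only for unscheduled scores outside every window. If those are not eligible, the carried score may be week 1 (day 8), aged 121 − 8 = 113 and 181 − 8 = 173 days.

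**Illustrative count** = 750 × failure × uptake
- Failure: 1 − 0.704 = 0.296 (2017-01, Protocol 5.3.4).
- Uptake: 15/16 = 0.9375 (2013-001, Protocol 5.3.1).
- 0.296 × 0.9375 = 0.2775; × 750 ≈ 208.
- With uptake of 50%, an assumption without a source in the documents: 0.296 × 0.50 = 0.148; × 750 = 111.

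The shift in the mean cannot be stated, because the documents give no Cdiff32 scoring rule or SD.

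**The case against.** The strongest case on the other side is that little depends on this. Cdiff32 is a descriptive other endpoint, and the carry-forward arises only if never-scheduled assessments count as missing. SAP 6.8 allows further analyses as needed, and SAP 7.1 states: "Subject listings of all data from the eCRFs as well as any derived variables will be presented". A reader with the listings should be able to separate observed from imputed scores. All of this stands, and it sets the priority. It does not close the gap: listings and as-needed analyses are not a pre-specified summary, and the alternative reading removes retreated subjects without saying so.

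Some stronger readings are tempting but unsupported:
- *The SAP breaks its own rule in 6.6.* That section governs safety events and also plans a combined analysis across both enemas. It is an analogy only.
- *The SAP is silent on unscheduled scores.* The closest-visit rule in 5.2.1 does not exclude them when they fall in a window, so the silence concerns only out-of-window scores.
- *The bias runs in a known direction.* It depends on which score is carried, and that is not fixed.
- *The affected number can be bounded from the other studies.* The 21.1% failure in 2015-01 follows two planned enemas. The 50% first-enema failure in 2013-001 rests on a success definition described without a stool test, whereas failure here needs a positive central-laboratory result. Multiplying further by the 11/14 second-enema success, to count subjects shown in recurrence despite success, adds the assumption that the recurrence-visit score is the one carried.

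**Conclusion.** The point holds as a gap in a stated imputation rule. Taken literally, the rule fills months 4 and 6 for most retreated subjects, and week 8 for those retreated early, with scores from before the second enema. Otherwise those subjects leave the means unannounced. This rests on the blank second-enema columns in both schedules, on Protocol 7.5 keeping only non-retreated failures on the original schedule, and on failure being determined within about 23 days of the latest qualifying onset.

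The size is illustrative: about 208 of 750 if the cap is reached, or 111 if uptake were 50%. It combines a failure rate and an uptake from different studies, and this trial's population is meant to be broader. A reader might infer that the efficacy or safety results are compromised. They are not, because no primary, secondary or safety conclusion uses Cdiff32. Priority is low.

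**What to change.** In SAP 6.8.3 and 7.3:
1. Do not carry Cdiff32 scores across a second enema in the main summary.
2. Show retreated subjects separately, including their recurrence-visit score.
3. Put observed-case summaries with n per visit beside any LOCF summary.
4. State whether out-of-window unscheduled scores enter LOCF, and whether assessments not scheduled after retreatment count as missing.

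Reconcile Protocol Table 10-1, 10.12 and 10.14.1 on whether Cdiff32 is collected after a second enema.

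The SAP part costs a few sentences and routine programming. If the reconciliation confirms no collection after a second enema, the protocol part is a clarification; if it concludes that Cdiff32 is collected, the schedule changes and the approvals in Protocol 13.14 apply. The statistical price is fewer subjects at later visits, with the remaining means leaning toward first-dose successes. The separate display and the n per visit make that visible.

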10.4. Optional Stool Samples for Additional Testing by Rebiotix

Subjects may agree (consent) to provide additional, optional stool samples to Rebiotix for research development activities. Subjects consenting to the Optional Stool Sample collection are requested to provide stool samples directly to Rebiotix at the following time-points:

- Screening (between the time of enrollment and prior to treatment)
- at the time of the 1- and 8-week office visits
- at the time of the 4-week, and at 4- and 6-month phone calls
- at the time of possible treatment failure symptoms
- at the 1-, 4-, and 8-weeks and 6-month phone calls after a second enema, if applicable

Subjects collect the samples at home in pre-labeled containers given to them by the study team. Rebiotix provides the study sites with kits containing all the materials for collecting and shipping the samples, including subject directions, container labels, and prepaid, pre-addressed mailing labels. Samples are identified by the label on the container that contains only the subject's study identification number and date/time of the sample; samples will not contain any personal information that would identify the subject. Samples may be stored for approximately five years. The stool samples will be used for research about the microorganisms in the human gut and the effects of microbiota restoration therapy on the gut microbiome. Some of the research will include testing for microorganisms (*Clostridium difficile* and vancomycin-resistant enterococci) both before and after receiving the study enema. Failure to send in a sample does not result in a protocol deviation, however subjects should be reminded of this request.

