10.8. Baseline Visit and Study Treatment Administration

IP/study drug should be ordered approximately four (4) business days in advance of the planned IP administration date, if not earlier.

The Baseline visit is performed on the day of the study treatment (IP) administration. IP administration must occur within 21 days of the Screening visit. Antibiotics for the control of CDI symptoms are continued until 24-72 hours before administration of the IP.

The following study activities/data will be collected at the Baseline visit prior to IP administration:

- Inclusion/exclusion criteria are confirmed including the following:
 - The control of symptoms during antibiotic use is confirmed by review of the subject diary (see **Section 7.3.1**)
 - Compliance to the washout period (discontinuation of the antibiotics for 24-72 hours prior to the Baseline visit) is confirmed
 - Stop date and time (AM/PM) of antibiotic
- Central laboratory blood sample collection; see **Table 10-2** for the list of tests. *NOTE: these results are not needed before proceeding to treatment per the protocol*
- Central laboratory stool sample collection; see **Table 10-2** for the list of tests. *NOTE: the results are not needed before proceeding to treatment per the protocol*
- Onsite urine pregnancy test for subjects of child bearing potential
- Assess vital signs: temperature, pulse, blood pressure, respiration
- Changes to concomitant medications since the last visit
- Review subject diary (see **Section 10.3**)
- Assess recurrence of CDI
- Assess for adverse events since enrollment
- Date and time of the last bowel movement prior to the enema
- Did the subject void his/her bladder prior to entering the administration room

Table 10-2: Baseline Testing Conducted by Central Laboratory

Test Name	Material Tested
Norovirus	Stool
Rotavirus	
Adenovirus	
Enteric pathogens (Shigella , Salmonella , Campylobacter , sorbitol-negative E. coli ., Aeromonas , Plesiomonas , Yersinia , and shiga toxins)	
Giardia antigen	
Cryptosporidium antigen	
Acid-fast staining (Cyclospora, Isospora)	
Ova and parasites	
Vancomycin-resistant enterococci (VRE)	
Methicillin-resistant Staphylococcus aureus (MRSA)	
Extended spectrum beta-lactamase (ESBL)-producing Enterobacteriaceae	
Vibrio	
Listeria	
Clostridium difficile	
Carbapenem-resistant Enterobacteriaceae Culture (CRE)	
CBC with Differential	Blood
HIV	

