5 BASELINE, SAFETY AND EFFICACY EVALUATIONS

5.1 Schedule of Events

Activity	Screening (Enrollment)	Baseline / Enema Administration (≤ 21 days from Screening)	Follow-up Visits: 1- and 8-Week (± 3 days) Assessments ¹	Follow-up Phone Assessment: Week 4 (± 3 days)	Follow-up Phone Assessment: 4 and 6 months (± 14 days)	Unscheduled Possible Recurrence Visit	Second Enema Administration ¹ (≤ 21 calendar days post Tx Failure)	Second Enema Follow-up Phone Assessment: 1-, 4-, and 8-week (± 3 days), and 6 months (± 14 days)
Informed consent obtained	X							
Demographics, medical history	X							
Prescribe/continue antibiotics for CDI symptom control	X							
Physical exam	X							
Stool sent to Rebiotix by subjects for testing and archiving (optional)	X		X	X	X	X		X
Central Lab CBC w/differential testing ³	X ³	X						
Central Lab CD4 testing	X ³							
Central Lab CMP & CRP testing	X							
C. difficile testing ⁴	X ⁴					X ⁴		
Central Lab stool and blood testing		X						
Urine pregnancy testing performed at site (if applicable)	X	X					X	
Cdiff32 Questionnaire	X	X	X		X	X		
Inclusion/exclusion criteria confirmed	X	X						
24-72hr washout period confirmed		X					X ⁷	
Enema administered		X					X	
Product complaint (if applicable)		X					X	
CDI symptoms assessed		X	X	X	X	X	X	X
Vital signs assessed	X	X				X	X	
Weight	X		X	X	X			X
Subject Diary discussed/reviewed	X	X	X ⁵					
Employment status assessed	X		X ⁶		X			
Concomitant medications	X	X	X	X	X	X	X	X
Adverse events assessed		X	X	X	X	X	X	X
Solicited events assessed ²		X	X ²					

¹ Documented treatment failures may receive a second RBX2660 enema.

² Solicited events are collected in the Subject Diary from the day of the baseline enema until the day prior to the 1-week Follow-up visit. The Subject Diary is reviewed at the 1-week Follow-up visit. Solicited events that increase in severity from Screening should be assessed for a possible adverse event.

³ Exclusion criteria for absolute neutrophil count and CD4 should be assessed based on the blood samples collected at the Screening visit.

⁴ Tested at the central laboratory

⁵ Subject Diary is reviewed only at the 1-week Follow-up visit.

⁶ Collected at the 8-week follow-up visit only.

⁷ If antibiotics were administered to manage CDI recurrence.

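### The VRE and C. difficile clearance analyses neither fix the pre-treatment reference sample nor require paired samples, so a change in who returns stool, and possibly of laboratory, could be reported as clearance

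*SAP*

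**What the plan says.** **Analysis text.** SAP 6.8.5 (VRE) and 6.8.6 (C. difficile) use laboratory values "based on submitted stool samples at Baseline and at 1-week, 4-weeks, 8-weeks" and 4 and 6 months. For VRE, these "will be assessed for all subjects to identify any trends in the clearance of vancomycin-resistant enterococci following enema treatment"; 6.8.6 has a parallel sentence for C. difficile. Neither subsection names a laboratory.

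**Stool at the Baseline visit.** Protocol 10.8 requires a sample under the item "Central laboratory stool sample collection; see" Table 10-2. That table is titled "Table 10-2: Baseline Testing Conducted by Central Laboratory", and its panel includes VRE and C. difficile. Table 10-1 schedules no other stool in the Baseline column.

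**Stool at follow-up.** The Table 10-1 row "Stool sent to Rebiotix by subjects for testing and archiving (optional" is marked at Screening, at every scheduled follow-up contact, at a possible-recurrence visit and after a second enema, but not at Baseline. Protocol 10.4 states: "Subjects may agree (consent) to provide additional, optional stool samples to Rebiotix for research development activities". A missed sample is not a deviation. The same section lists a pre-treatment sample, "Screening (between the time of enrollment and prior to treatment", and says that C. difficile and VRE will be tested in this stream before and after the enema.

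**Central retesting.** After treatment, the schedule has central C. difficile testing only at an unscheduled possible-recurrence visit. It has no central VRE retest.

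**The concern.** A clearance analysis needs one pre-treatment value per subject, a later value from the same subject, and the same measurement at both times. The SAP secures none of these. It does not say which sample is the starting value, which laboratory's results are used, or that only subjects with both samples enter. It gives no definition of clearance and no rule for unreturned samples; SAP 7.3 says only that nothing is imputed apart from the Cdiff32 scores and the adverse-event date rules.

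The follow-up subset selects itself, through separate consent and then through actually sending a sample. If persisting carriers send fewer samples than others, positivity falls without anyone clearing the organism. If the starting value is also from another laboratory, a difference in assay sensitivity is added. At stake is the reading of other objectives 5 and 6 (protocol 6.3, SAP 2.3).

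**Working it through.** The plan states no clearance rate, assay performance or return rate, so there is no figure to reproduce. The check has two parts: the documents set side by side, then an illustration in which every numerical input is assumed.

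**1. Which sample is the reference?**

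| Points to the central sample on day 1 | Points to the optional Screening sample |
|---|---|
| SAP 6.8.5 and 6.8.6 say Baseline, while 6.8.2 and 6.8.3 say Screening | Protocol 6.7 items 5 and 6, SAP 5.6 item 6 and the 6.8.6 heading say Screening |
| SAP Table 1 separates Screening (days -20 to -1) from Baseline (day 1) | SAP 6.3 lets Baseline assessments fall up to 20 days before treatment |
| The optional row has no mark at the Baseline visit | SAP 6.8.5 and 6.8.6 speak of submitted samples, which fits stool that subjects send in |
| SAP 5.6 item 5 drops Screening and follows carriers at Baseline | Protocol 10.4 plans testing before and after the enema within the optional stream |

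The literal reading is the left column, but the documents do not settle it. For C. difficile there is a third candidate. SAP 5.1 marks a test at Screening, footnoted "Tested at the central laboratory", that protocol Table 10-1 does not have.

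**2. Change of subjects (either reading).** Assume a perfect test, no true change, carriage p, and return rates r1 for carriers and r0 for non-carriers. Without pairing:

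follow-up positivity = p·r1 / (p·r1 + (1 − p)·r0)

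With r0 = 0.50:

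| p | r1 = 0.50 | r1 = 0.40 | r1 = 0.25 |
|---|---|---|---|
| 20% | 20% | 0.08/0.48 = 16.7% | 0.05/0.45 = 11.1% |
| 40% | 40% | 0.16/0.46 = 34.8% | 0.10/0.40 = 25.0% |

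Equal return rates give no shift. If carriers return more samples than non-carriers, the shift reverses.

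**3. Change of laboratory (only if Baseline means the central sample).** Take subjects positive in the first laboratory, with true clearance zero. Assume sensitivity 0.95 there, specificity 0.98 in both laboratories, and test errors independent between samples.

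PPV = 0.95p / [0.95p + 0.02(1 − p)]

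- p = 20%: 0.190/0.206 = 0.922
- p = 40%: 0.380/0.392 = 0.969

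apparent clearance = 1 − [PPV × follow-up sensitivity + (1 − PPV) × 0.02]

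| Follow-up sensitivity | p = 20% | p = 40% |
|---|---|---|
| 0.95 (same laboratory) | 12.2% | 7.8% |
| 0.90 | 16.8% | 12.7% |
| 0.80 | 26.1% | 22.4% |
| 0.70 | 35.3% | 32.1% |

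Keeping one laboratory removes about 5 to 24 points. The 8% to 12% floor from test error remains in any analysis restricted to subjects who first tested positive.

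**The case against.** A reader might infer that the plan, as written, compares a central-laboratory value with sponsor values, so that a change of assay is built in. The documents do not support that. The SAP names no laboratory. Protocol 10.4 provides a comparison within one stream. The endpoints largely say Screening, and SAP 6.3 allows Baseline to reach back to that visit. The two words are also used loosely elsewhere: objective 3 speaks of change from Baseline microbial composition, while SAP 6.8.2 starts from Screening and Table 10-2 lists no microbiome test. The sponsor stream's laboratory and assay are not described, so a difference in sensitivity is possible but not shown. This part of the objection stands, and the laboratory effect must remain conditional.

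It can also be said that these are other objectives, assessed only for trends, with no test or decision resting on them. That limits the weight of the point and rules out saying that the objectives cannot be read at all.

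The objection does not reach the change of subjects. Even within one stream, the text says all subjects, follow-up comes from those who consent and return stool, and no paired denominator or missing-sample rule is given. Nor does it explain why the heading and text of 6.8.6 disagree on the starting visit.

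**Conclusion.** The point holds in a conditional form. The reference sample is ambiguous, and the analysis is not restricted to paired samples. A change in who returns stool could be reported as clearance under either reading; a change of laboratory or method could be only if Baseline means the central sample.

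The size cannot be derived from the documents. The ranges above (20% falling to 16.7%-11.1% through differential return; 13%-35% apparent clearance with a less sensitive second laboratory, against 8%-12% with one) rest wholly on assumed carriage, return rates, sensitivity and specificity. They show that the effect can be material, not that it will occur.

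A reader might extend the laboratory concern to the microbiome analysis in SAP 6.8.2. It does not apply there, because that analysis already starts from Screening and the central panel has no microbiome test. The consequence is confined to exploratory objectives 5 and 6; the primary safety endpoint and the secondary efficacy endpoints are not affected.

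**What to change.** In SAP 6.8.5 and 6.8.6:

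- Take the pre-treatment value and carrier status from the optional pre-enema (Screening) sample in the sponsor stream, in line with protocol 6.7.
- Define clearance. At each visit, analyse it only in subjects positive on that sample who also have the visit sample tested by the same laboratory and method.
- Report paired counts, with the number of samples returned and missing at each visit.
- Show the central-laboratory Baseline results separately, with their agreement with the sponsor-stream results.

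Reconcile Screening with Baseline, carriers with all subjects, concentration with presence, and the Screening C. difficile mark that is in SAP 5.1 but not in protocol Table 10-1. SAP 6.8.2 needs no change for the laboratory issue.

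The cost is SAP wording, with three limits to state openly:

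- Paired denominators will be smaller, a limit that optional sampling already sets.
- The Screening sample may be taken while the subject is still on CDI antibiotics, whereas the Baseline visit follows the washout. A change after antibiotics stop could then look like clearance or acquisition, and this should be said when the trends are interpreted.
- Pairing does not correct for subjects whose decision to return a later sample depends on whether they still carry the organism, which is why the missing counts are needed.
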